## **Protocol Template**

Sponsor: Menarini Pharmaceutical Study Code: MEIN/19/ZoNe-HYP/001

Protocol Version\_1 of 16/07/2020

Number of Centers	
List of Countries	European Union countries
	This study will last 12 weeks.
	Screening Visit (Visit 1, week -4)
	Uncontrolled hypertensive patients receiving treatment with any ACE-i or
	BBs including ZOF 30 mg or NEB 5 mg will be screened for eligibility.
	Run-in period (4 weeks): from Visit 1 (Week-4) to Visit 2 (Week 0)
	Eligible patients from Screening will enter the run-in period on the same day.
	Patients previously receiving ZOF or any other ACE-i will enter into the
	run-in period with ZOF monotherapy while patients receiving NEB or any
	other BBs will enter into the Run–in period with NEB monotherapy in a 1:1
Study Duration (specify	ratio.
different study phases):	Assessment period (8 weeks): from Visit 2 (Week 0) to Visit 3 (Week 8)
	Patients experiencing uncontrolled BP after 4 weeks of monotherapy, will be
	given the extemporaneous combination of NEB 5 mg and ZOF 30 mg at
	Week 0 (Visit 2) and will be assessed for 8 weeks (assessment period).
	Patients with controlled BP (sitting SBP/DBP ≤130/80 mmHg) and/or
	patients who do not tolerate the treatment at Week 0 (Visit 2) will be
	withdrawn from the study.
	Only uncontrolled BP patients, whose adherence to the treatment (actual
	doses taken compared to planned doses to be taken) ranges from 80% to
	120%, will enter the assessment period.
Patient Study Phases	For patients completing the study, participation will last up to 12 weeks:
Duration	4 weeks of run-in period (monotherapy)
	8 weeks of assessment period (extemporaneous combination)

Identification Number: FORM-000050125

Previous Doc Number:
CTWI10A

Version Number: 1.0, CURRENT

### **Protocol Template**

Sponsor: Menarini Pharmaceutical Study Code: MEIN/19/ZoNe-HYP/001

Protocol Version\_1 of 16/07/2020

The primary endpoint will be assessed before and after assessment period at Week 8, by a paired t-test using the ITT population and the Per protocol (PP) population. All other secondary endpoints will be assessed before (Week 0) and after treatment (at Week 8).

Statistical Assumptions

A total sample size of 216 patients is required to achieve 90% power at a 5% significance level assuming a difference in mean DBP from baseline to 8 weeks of 4 mmHg and a standard deviation (SD) for this difference of 10 mmHg. The mean change in DBP for the null hypothesis is set equal to 2 mmHg.

Identification Number: FORM-000050125

Previous Doc Number: CTWI10A

Version Number: 1.0, CURRENT

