# combination (actual doses taken versus planned doses to be taken) To evaluate the safety and tolerability of the ZOF and NEB monotherapies, and the extemporaneous combination of NEB 5 mg and ZOF 30 mg after 8 weeks of treatment **Exploratory objective:** To assess the antihypertensive efficacy at different time points in patients who (1) received NEB or ZOF monotherapies before the run-in period, (2) received any other ACE-i or BB monotherapies before the run-in period To assess the antihypertensive effect on patients, based on their hypertension grade, presence or absence of hypercholesterolemia, presence or absence of diabetes at Visit 2 and Visit 3 Primary endpoint: Change in mean sitting DBP between Week 0 (Visit 2) and Week 8 (Visit 3) Secondary endpoint: Change in mean sitting SBP between Week 0 (Visit 2) and Week 8 (Visit 3) Total number and proportion of patients achieving the BP goal (sitting BP ≤130/80 mmHg) at Week 0 (Visit 2) and Week 8 (Visit 3)

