#### 14.5.7 Safety Analysis

#### **Adverse Events:**

Adverse events recorded during the study will be mapped to a system organ class (SOC) and preferred term (PT) using the current Medical Dictionary for Regulatory Activities (MedDRA). Treatment-emergent adverse events are defined as new AEs that occur on or after the date/time of the first administration of study medication or worsen if an AE started prior to the start of first administration of study medication.

All the AEs will be presented with the following:

- Number of cases
- Number of patients with AE
- Percentage of patients with AE

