#### 18. SAFETY OUTCOMES

All outputs for safety outcomes will be based on the Safety Analysis Population.

There will be no statistical comparisons between the treatment groups for safety data, unless otherwise specified with the relevant section.

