#### 18.1. ADVERSE EVENTS

Adverse Events (AEs) will be coded using Medical Dictionary for Regulatory Activities (MedDRA) central coding dictionary, Version 23.1.

Treatment emergent adverse events (TEAEs) are defined as AEs that started or worsened in severity on or after the first dose of study medication (Combination therapy).

See Appendix 2 for handling of partial dates for AEs. In the case where it is not possible to define an AE as treatment emergent or not, the AE will be classified by the worst case; i.e. treatment emergent.

An overall summary of number of patients within each of the categories described in the sub-section below, will be provided as specified in the templates. Listings will include TEAEs and Non-TEAEs.

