#### **18.1.1.** ALL TEAES

Incidence of TEAEs will be presented by System Organ Class (SOC) and Preferred Term (PT) and broken down further by maximum severity and relationship to study medication.

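### The SAP gives the monotherapy safety objective no adverse-event summary, and any run-in percentage that is tabulated would cover 4 weeks against 8 for the combination

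*Protocol*

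**What the plan says.** **Aim.** Protocol Section 7 sets out to assess the safety of the combination against each monotherapy. The secondary objective in the synopsis, carried into Protocol Section 6 and SAP 2.2, is "To evaluate the safety and tolerability of the ZOF and NEB monotherapies, and the extemporaneous combination". The synopsis sentence on timing, "All other secondary endpoints will be assessed before (Week 0) and after treatment (at Week 8", says when secondary endpoints are assessed. It does not say how AEs are counted.

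**Length of each phase.** The synopsis gives "4 weeks of run-in period (monotherapy" and "8 weeks of assessment period (extemporaneous combination".

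**AE measure.** Protocol 14.5.7 reports all AEs as number of cases, number of patients, and "Percentage of patients with AE". SAP 18.1.1 says "Incidence of TEAEs will be presented by System Organ Class (SOC) and Preferred Term (PT", with a further split by severity and drug relationship.

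**Scope.** SAP 18.1 defines treatment-emergent AEs (TEAEs) as "AEs that started or worsened in severity on or after the first dose of study medication (Combination therapy" and mentions non-TEAEs only in connection with listings. SAP 18 states "All outputs for safety outcomes will be based on the Safety Analysis Population", and SAP 5.3 admits to that population only patients with at least one combination dose. SAP 18 plans no statistical safety comparison between treatment groups unless a section says otherwise.

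**Exposure.** SAP 14 and 14.1 derive days on drug for both phases. Nothing in SAP 18 uses them.

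**The concern.** A stated secondary objective should end in a table. For AEs on NEB alone and ZOF alone, the SAP specifies none. The patients most informative about monotherapy tolerability, those who stopped during the run-in or were withdrawn at Visit 2 for intolerance, never enter the Safety population.

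There is a second risk if the gap is filled informally. A programmer could reasonably produce run-in AE percentages next to the combination percentage, because three places point that way:
- Protocol 14.5.7 speaks of all AEs.
- Protocol 10.2 counts from the first dose of study treatments, and Protocol Section 9 treats run-in NEB and ZOF as such.
- SAP Appendix 1 defines NEB and ZOF output groups.

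The two percentages would then cover different lengths of observation with no person-time adjustment. A real excess on the combination could not be separated from longer follow-up.

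**Working it through.** The documents state no AE rate, so there is no AE figure of the plan's own to reproduce. The 4-week percentage p below is an assumption, shown over a range.

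**Step 1: what the SAP yields for a run-in AE.**
- The event starts before the first combination dose. It is not a TEAE under SAP 18.1 unless it worsens later, so it is absent from the SAP 18.1.1 tables.
- If the patient goes on to the combination, the event appears in a listing.
- If the patient leaves on monotherapy, SAP 5.3 and SAP 18 together exclude the patient from safety outputs. SAP 8 describes tables, figures and listings together as the planned presentations. Read literally, the event may therefore not reach a safety listing either.
- The planned loss over the whole study is 290 − 216 = 74 patients. The documents do not split this into screening failures, run-in leavers and later drop-outs, so the number affected is unknown.

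**Step 2: the effect of unequal time, if run-in percentages are tabulated.** Assume a constant hazard, equal in both phases. A 4-week risk p gives an 8-week risk of 1 − (1 − p)², so the ratio is [1 − (1 − p)²] / p = 2 − p.

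**Step 3: two possible rates per 100 patient-weeks.**
- Time counted to the first event or the end of the phase: 100 × [−ln(1 − p)] / 4 in both phases, ratio 1.00.
- Full phase duration, which is what SAP 14.1 derives: 100p / 4 in the run-in and 100 × [1 − (1 − p)²] / 8 on the combination, ratio 1 − p/2.

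| p (4 weeks) | 8-week % | Ratio of % | Rate, time to first event (both phases) | Rate, full duration: run-in / combination | Ratio |
|---|---|---|---|---|---|
| 5% | 9.75% | 1.95 | 1.28 | 1.25 / 1.22 | 0.975 |
| 10% | 19% | 1.90 | 2.63 | 2.50 / 2.38 | 0.95 |
| 20% | 36% | 1.80 | 5.58 | 5.00 / 4.50 | 0.90 |
| 50% | 75% | 1.50 | 17.33 | 12.50 / 9.38 | 0.75 |

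Dividing patients with an AE by the full SAP 14.1 duration would therefore replace one bias with a smaller one in the opposite direction.

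**Step 4: visit windows.** These are ±2 days at Visit 2 and ±3 days at Visit 3. With h = −ln(1 − p)/28, the ratio is [1 − exp(−h·d₂)] / [1 − exp(−h·d₁)].
- From d₁ = 30, d₂ = 53 to d₁ = 26, d₂ = 59, the ratio runs from 1.73 to 2.20 at p = 5%.
- Over the same range it runs from 1.62 to 2.00 at p = 20%.

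**Step 5: what the equal-hazard model leaves out.** Patients who do not tolerate monotherapy are withdrawn at Visit 2, which lowers the combination percentage. Some patients were already on the same drug at Visit 1, which would tend to lower the run-in percentage. The documents give no figures for either effect.

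**The case against.** A reader might infer that the trial will report the combination with nearly twice the AE percentage of the monotherapies. The documents do not support that. The SAP specifies no monotherapy AE percentage, so the contrast is not a planned output. The ratio also needs a constant and equal hazard, and selection at Visit 2 works against it by an unknown amount.

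The rest of the case for the plan is as follows:
- *The protocol's analysis-variable table (14.4) names only the combination in its safety row.* True, and it agrees with the SAP. It also leaves the monotherapy part of the objective without an analysis.
- *The NEB and ZOF labels in Appendix 1 are needed anyway* for exposure, compliance and vital signs, which the SAP plans for both phases. True. The labels show that a run-in AE table is possible, not that one is planned.
- *SAP 18 plans no statistical comparison for safety.* A descriptive display over unequal periods can mislead just as a test can.
- *Both phase lengths are stated and exposure days are reported.* A reader can see the imbalance, but cannot recover time to first event from summary tables.
- *Disposition is shown for the Enrolled population (SAP 9.1),* so withdrawals and reasons during the run-in should be counted. That gives a reason for leaving, not an AE summary.

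**Conclusion.** The gap is real and comes from the SAP's own rules: the objective on monotherapy safety has no AE summary, and patients who left on monotherapy are excluded from safety outputs. This part rests on no numerical assumption.

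The distortion from unequal follow-up is conditional. It arises only if run-in percentages are tabulated. Its size, 2 − p, holds only for a constant, equal hazard and nominal phase lengths. It is close to twofold for uncommon events and well short of that for common ones. With selection at Visit 2 acting the other way, the direction of the net bias cannot be stated. Crude percentages would show neither a true excess nor its absence.

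The primary endpoint is untouched. The change is worth making because a stated secondary objective is otherwise unanswered for AEs and the repair is cheap.

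**What to change.** In SAP 18.1, with a matching exception to the Safety-population rule in SAP 18:

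1. Add AE summaries (any, drug-related, serious, leading to stop) for NEB run-in and ZOF run-in, in all patients who took at least one run-in dose. Assign AEs to phase by onset date. A run-in event that worsens on the combination still counts there, as SAP 18.1 already provides.
2. For each run-in group and for NEB+ZOF, give first events per 100 patient-weeks with an exact 95% confidence interval. Count time to the first event or the end of that phase, not the full SAP 14.1 duration.
3. Give the percentage of patients with onset in Days 1–28 of the combination beside the 4-week run-in percentage, with both denominators shown.
4. State that the comparison is descriptive, because patients entering the combination phase had tolerated monotherapy.

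Keep the 8-week crude percentage as the description of the combination alone. Record in SAP 3.3 how the SAP's TEAE definition relates to the wider wording in Protocol 10.2.

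The cost is SAP wording and a few more table lines. SAP 14 already takes exposure dates from the eCRF, and SAP Appendix 2 already relies on AE start dates, so no new data or visits are needed. The rate assumes a roughly constant hazard. The 28-day comparison does not, which is why both are shown. The change should be made before database lock, because Protocol 14.7 treats analyses that were not prespecified and are run after lock as additional or exploratory.

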## **Protocol Template**

Sponsor: Menarini Pharmaceutical Study Code: MEIN/19/ZoNe-HYP/001

Protocol Version\_1 of 16/07/2020

# 3. LIST OF ABBREVIATIONS AND DEFINITION OF TERMS

ABBREVIATION	DEFINITION
ACE-i	angiotensin converting enzyme-inhibitors
ADR	adverse drug reaction
AE	adverse Event
AEOSI	adverse events of special interest
ALT	alanine aminotransferase
AST	aspartate aminotransferase
ATC	anatomical therapeutic chemical
ВВ	beta blocker
BP	blood pressure
CRO	contract research organization
DBP	diastolic BP
EC	ethics Committee
ECG	electrocardiogram
eCRF	electronic case report form
EOT	end of treatment
FDC	Fixed-dose combination
GCP	good clinical practice
HA	health authority
ICF	informed consent form
ICH	International Council for Harmonisation
ICSR	individual case safety report
ITT	Intent-to-treat
NEB	Nebivolol
NSAE	Nonserious AE
PI	Principal Investigator

Identification Number: FORM-000050125

Previous Doc Number: CTWI10A

Version Number: 1.0, CURRENT

## **Protocol Template**

Sponsor: Menarini Pharmaceutical Protocol Version\_1 of 16/07/2020 Study Code: MEIN/19/ZoNe-HYP/001

PP	per protocol
PT	preferred term
SAE	serious adverse event
SAP	statistical analysis plan
SBP	systolic BP
SD	standard deviation
SmPC	summary of product characteristics
SOC	system organ class
SOP	standard operating procedure
SUSAR	suspected unexpected serious adverse reaction
TMF	trial master file
ULN	upper limit of normal
ZOF	zofenopril calcium

Identification Number: FORM-000050125

[figure not shown]
Previous Doc Number: CTWI10A

Version Number: 1.0, CURRENT

Sponsor: Menarini International Operations Luxembourg Study Code: MEIN/19/ZoNe-HYP/001

Protocol Version\_1 of 16/07/2020

4. STUDY SCHEME

BP: Blood pressure, NEB: Nebivolol, ZOF: Zofenopril calcium, ACE-i: Angiotensin converting enzyme-inhibitors, BB: Beta blockers

- Patients meeting the eligibility criteria at Screening (Visit 1), will enter the run-in period on the same day
- Patients who were on ZOF or NEB treatment at Screening, will continue to receive the same drugs; the
  patients on any other ACE-i will start ZOF and patients who were on any other BB will start NEB from the
  same day
- Only patients with uncontrolled BP (sitting SBP/DBP >130/80 mmHg) and whose adherence to the treatment ranges from 80% to 120%, will enter the assessment period to receive the extemporaneous combination of NEB and ZOF; while the patients with controlled sitting BP (SBP/DBP ≤130/80 mmHg) and/or the patients who do not tolerate the treatment and patients with uncontrolled BP whose adherence to the therapy do not range from 80% to 120%, will be withdrawn from the study.

Identification Number:
FORM-000050125
Previous Doc Number:
CTWI10A
Version Number:

1.0, CURRENT

Sponsor: Menarini International Operations Luxembourg
Study Code: MEIN/19/ZoNe-HYP/001
Protocol Version\_1 of 16/07/2020

# 4.1 Study Flow Chart

Study Procedures/ Assessments	Visit 1 (Week -4)	Visit 2 (Week 0) a	Visit 3 (Week 8) a
	Screening +	Start of	End of
	Start of Run-in	Assessment	Assessment
	Period b	Period	Period
Informed consent	X		
Inclusion/exclusion criteria	Х		
Medical history	Х		
Prior medication	Х		
Demography (age, sex, race)	Х		
Concurrent diseases and medical conditions	Х	Х	Х
Antihypertensive treatment with NEB or ZOF monotherapy c	Х		
Study drug dispensing d		X	
Study drug return and accountability (Compliance assessment)		X e	X f
Concomitant medications	Х	Х	Х
Urine pregnancy test	Х	Х	Х
Physical examination	Х	Х	Х
Vital signs	Х	X	Х
Laboratory test 	X		Х
Blood pressure	X	X	Х
ECG	X	X	Х
AE/SAE assessment	Х	Х	X h

Identification Number: FORM-000050125

Previous Doc Number: CTWI10A

Version Number: 1.0, CURRENT

#### **Protocol Template**

Sponsor: Menarini Pharmaceutical Study Code: MEIN/19/ZoNe-HYP/001

Protocol Version\_1 of 16/07/2020

ACE-i: Angiotensin converting enzyme-inhibitors; AE: Adverse event; BB: Beta blockers; ECG: electrocardiogram; EOT: End of treatment; NEB: nebivolol; SAE: serious adverse event; ZOF: zofenopril calcium

- a: For Visit 2, a window of ±2 days will be allowed at Week 0; and for Visit 3, a window of ±3 days will be allowed at Week 8
- b: Patients meeting the eligibility criteria at Screening, will enter the run-in period on the same day
- c: Patients on ZOF 30 mg or NEB 5 mg at Screening will continue the same therapy. Patients on any other ACE-i or BBs at Screening will be assigned to monotherapy with ZOF 30 mg or NEB 5 mg, respectively
- d: Patients will be provided with the extemporaneous combination of NEB 5 mg with ZOF 30 mg
- e: Adherence to monotherapies will be checked at the beginning of Visit 2
- f: Adherence to the extemporaneous combination of NEB 5 mg with ZOF 30 mg will be checked at the end of Visit 3
- g: To ensure patient safety, the patients will be contacted over phone within 24 hours, in case of any abnormality and clinically relevant laboratory test according to the Investigator's judgement at any visit
- h: Patients having any ongoing AE/SAE at the end of the treatment, will be followed for further 2 weeks via a phone call to check about the status of the AE/SAE

## 5. STUDY RATIONALE AND BACKGROUND INFORMATION

Based on office blood pressure (BP), the global prevalence of hypertension was estimated to be 1.13 billion in 2015, with a prevalence of over 150 million in central and eastern Europe. The overall prevalence of hypertension in adults is around 30% to 45%.1 Elevated BP was the leading global contributor to premature death in 2015, accounting for almost 10 million deaths and over 200 million disability-adjusted life years.2

The 2 well-established strategies to lower BP are lifestyle interventions and drug treatment.3

The drug treatment of hypertension is found on very solid evidence, supported by the largest number of outcome-based randomized clinical trials (RCTs) in clinical medicine. Meta-analyses of RCTs including several hundred thousand patients have shown that a 10 mmHg reduction in systolic blood pressure (SBP) or a 5 mmHg reduction in diastolic blood pressure (DBP) is associated with significant reductions in all major cardiovascular (CV) events by approximately 20%, all-cause mortality by 10% to 15%, stroke by approximately 35%, coronary events by approximately 20%, and heart failure by approximately 40%.45

Identification Number: FORM-000050125

Previous Doc Number:
CTWI10A

Version Number: 1.0, CURRENT

#### **Protocol Template**

Sponsor: Menarini Pharmaceutical Study Code: MEIN/19/ZoNe-HYP/001

Protocol Version 1 of 16/07/2020

Guidelines have generated a variety of different strategies to initiate and escalate BP-lowering medication to improve BP control rates. In previous guidelines, the emphasis was on initial use of different monotherapies, increasing their dose, or substituting for another monotherapy. However, increasing the dose of monotherapy produces little additional BP-lowering and may increase the risk of adverse effects. For these reasons, more recent guidelines have increasingly focused on the stepped care approach, initiating treatment with different monotherapies and then sequentially adding other drugs until BP control is achieved.3

Despite this, BP control rates have remained poor worldwide, only 40% of patients with hypertension being treated and of these, only 35% being controlled to a BP of <140/90 mmHg.1

This has become an even more pressing matter based on the new evidence. As the current guidelines are recommending more stringent BP targets (on treatment values of ≤130/80 mmHg in the general population and <140/90 mmHg in older hypertensive people) provided that the treatment is well tolerated, it will make the achievement of BP control even more challenging.3 Patients with hypertension are generally treated with multiple pharmaceutical products, fixed-dose combinations (FDCs) have generated increasing interest and have been recommended in treatment guidelines due to advantages in dosing and compliance, leading to improved treatment outcomes.

One of the main reasons why the current treatment strategy has failed to achieve better BP control rates is the insufficient use of combination treatment.

Blood pressure is a multiregulated variable depending on many compensating pathways. Consequently, combinations of drugs, working through different mechanisms, are required to reduce BP in most people with hypertension. Thus, monotherapy is likely to be inadequate in most patients. Indeed, almost all patients in RCTs have required combinations of drugs to control their BP.6

Nebivolol (NEB, a beta blocker [BB]) and zofenopril calcium ([ZOF], an angiotensin converting enzyme [ACE]-inhibitor [ACE-i]) are antihypertensive drugs widely prescribed as monotherapies in the real world. Both drugs have specific benefit-risk profiles with different mechanisms of action. Beyond its beta receptor-blocking effects, nebivolol has a vasodilatory action,

Identification Number: FORM-000050125

Previous Doc Number:
CTWI10A

Version Number: 1.0, CURRENT

#### **Protocol Template**

Sponsor: Menarini Pharmaceutical Study Code: MEIN/19/ZoNe-HYP/001

Protocol Version 1 of 16/07/2020

presumably mediated by its ability to increase availability of vascular endothelial nitric oxide. Nebivolol shows a distinct hemodynamic profile including reduced peripheral vascular resistance and a neutral impact on cardiac output, metabolic profile, and overall tolerability. Because this mechanism of action appears to be independent of its renin inhibitory effects, an additional BP-lowering effect could be anticipated when nebivolol is combined with a blocker of the renin-angiotensin system.7

Zofenopril calcium has been widely investigated for the treatment of patients with hypertension and its BP-lowering effect has been compared with either placebo or with all the classes of anti-hypertensive drugs currently recommended for the treatment of hypertension. Overall, clinical studies in patients with mild to moderate essential hypertension found that treatment with zofenopril calcium 30 to 60 mg/day was at least as effective and well tolerated as usual therapeutic dose regimens of other most widely used anti-hypertensive drugs.8

Despite data showing an added effect in providing NEB or ZOF to other anti-hypertensive treatment,9 there is scarce evidence at the moment on the anti-hypertensive effect of NEB/ZOF combination versus each monotherapy.

This study aims to assess the efficacy of NEB/ZOF, provided as an extemporaneous combination, in reducing systolic and diastolic BP in Grade 1 to 2 hypertensive patients versus each monotherapy.

This study will be conducted in compliance with the protocol, Good Clinical Practice (GCP), and the applicable regulatory requirements.

